**Table 16 Solicited local adverse events**

Pain at injection site
Redness * at injection site
Swelling at injection site

\* In case it is not possible to determine the extent of redness on darkly pigmented skin, it will be reported as uninterpretable on the Diary Card and in eSource.

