#### 15.2.1. DERIVATIONS

Based on the aforementioned variables, the following variables will be derived:

- End date after Day 6 relative day:
  - o Calculated relative to the most recent vaccination (refer to Section 6.1: Reference Start Date and Relative Day).
- Duration of solicited sign or symptom (refer to Section 6.7.3: Duration):
  - o If ongoing after Day 6:  
End date/day: End date after Day 6 as recorded in eSource.

Document: CHAD3-004-EBO-Z\_Interim\_Final\_SAP\_v2\_0  
Author: PPD Version Number: 2.0 Version Date: 14JUN2017

Template No: CS\_TP\_BS016 – Revision 3  
Effective Date: 01May2012

Reference: CS\_WI\_BS005

Start date/day: Start date of sign or symptom (derived from the first study day where sign or symptom is present relative to the study vaccination date). o If not ongoing after Day 6:

End date/day: Last date of sign or symptom (derived from the study day where sign or symptom is present relative to the study vaccination date).

Start date/day: Start date of sign or symptom (derived from the first study day where sign or symptom is present relative to the study vaccination date).

- Relationship to study vaccine for local solicited signs or symptoms:
  - o All local signs or symptoms will be regarded as related to study vaccine.
- Intensity for fever, redness and swelling:

Refer to APPENDIX 4: Solicited Adverse Event (AE) Intensity Grading, for the required intensity grade assignment for fever, redness and swelling.

- Dose at onset:
  - o Dose at onset will be assigned for all solicited AEs and is defined as the most recent dose prior to the onset of the AE:
    - EBO-Z:
      - Day 0.
      - Month 6.
    - Nimenrix:
      - Day 0.
      - Month 6.

---

Document: CHAD3-004-EBO-Z\_Interim\_Final\_SAP\_v2\_0  
Author: PPD Version Number: 2.0 Version Date: 14JUN2017

Template No: CS\_TP\_BS016 – Revision 3  
Effective Date: 01May2012

Reference: CS\_WI\_BS005

- MedDRA System Organ Class as well as Preferred Term will be assigned based on Table 6: Solicited Adverse Events MedDRA Coding, below.

Table 6: Solicited Adverse Events MedDRA Coding

Solicited AE	MedDRA System Organ Class	MedDRA Preferred Term
Redness	Skin and subcutaneous tissue disorders	Erythema
Swelling	General disorders and administration site conditions	Swelling
Pain	General disorders and administration site conditions	Pain
Fever	General disorders and administration site conditions	Pyrexia
Headache	Nervous system disorders	Headache

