#### 15.2.2. ALL SOLICITED ADVERSE EVENTS

The following listing is planned for presentation for the Total Vaccinated Cohort:

- Solicited AEs.

The following tables are planned for presentation for the Total Vaccinated Cohort:

- Overview of Solicited AEs:
  - Number and percentage (%) of subjects in each of the following categories:
    - Solicited AE.
    - Solicited severe (grade 3) AE.
    - Solicited related AE.
    - Solicited severe (grade 3) related AE.
    - Solicited local AE.

Document: CHAD3-004-EBO-Z\_Interim\_Final\_SAP\_v2\_0  
 Author: PPD Version Number: 2.0 Version Date: 14JUN2017

Template No: CS\_TP\_BS016 – Revision 3  
 Effective Date: 01May2012

Reference: CS\_WI\_BS005

- Severe (grade 3) solicited local AE.
- Solicited general AE.
- Severe (grade 3) solicited general AE.
- Related solicited general AE.
- Severe (grade 3) related solicited general AE.
- Solicited AE leading to premature study withdrawal.
- Severe (grade 3) solicited AE leading to premature study withdrawal.
- Related solicited AE leading to premature study withdrawal.
- Severe (grade 3) related solicited AE leading to premature study withdrawal.
- o Percentage (%) of subjects will be calculated relative to the total number of subjects in the relevant analysis cohort, per treatment group with returned diary cards.
- o A 95% confidence interval (CI) for the proportion of subjects with AEs in each category will be obtained by using the exact binomial option.
- o Subjects with multiple events in each category are counted only once in each category.
- Incidence of solicited AEs:
  - o Number and percentage (%) subjects with solicited AEs summarised by category and sign or symptom.
- Incidence of solicited AEs by severity:
  - o Number and percentage (%) subjects with solicited AEs summarised by category, sign or symptom and severity.
  - o This table will be repeated for related solicited AEs (including general solicited AEs only).
- Incidence of solicited AEs by relationship:
  - o Number and percentage (%) subjects with solicited AEs summarised by category, sign or symptom and relationship.
- Duration of fever (days):
  - o Descriptive statistics for the duration of fever will be provided, based on all subjects with at least one fever event reported.
- Onset Day of Fever during 7-day Follow-up Period After Vaccination on Day 0

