  - o Number and percentage (%) subjects with solicited fever summarised by earliest onset day (Day 0 to Day 6) following Day 0 study vaccination.
  - o Subjects with multiple events are considered only once at the earliest onset day. o % is based on the number of subject who reported fever in each category.

The following figures are planned for presentation for the Total Vaccinated Cohort:

- Reactogenicity events:
  - o Percentage of subjects presenting solicited AEs along with the 95% CI will be presented for all solicited events as well as Grade 3 or 4 events on the same figure (nested bar chart). o The bars will be presented separately for each treatment group. o This figure will be presented separately for

Document: CHAD3-004-EBO-Z\_Interim\_Final\_SAP\_v2\_0

Author: PPD Version Number: 2.0 Version Date: 14JUN2017

Template No: CS\_TP\_BS016 – Revision 3

Reference: CS\_WI\_BS005

Effective Date: 01May2012

- the local and general solicited AEs. o This figure will be repeated for the pooled data following the EBO-Z vaccination.
- Fever incidences per study day following Day 0 vaccination:
  - o Percentage of subjects presenting solicited fever along with the 95% CI will be presented for all solicited fever events as well as Grade 3 or 4 fever on the same figure (nested bar chart).
  - o The figure will be presenting the earliest study of fever onset. o The bars will be presented separately for each treatment group. o These figures will only include solicited fever within the reporting period following Day 0 vaccination.

For all solicited AEs the categories and signs or symptoms will be sorted as listed below:

Local:

- o Pain. o Redness.
- o Swelling.
- General:
  - o Fever. o Fatigue (only applicable to age strata: 13 to 17 years of age and 6 to 12 years of age).
  - o Gastrointestinal symptoms (only applicable to age strata: 13 to 17 years of age and 6 to 12 years of age).
  - o Headache (only applicable to age strata: 13 to 17 years of age and 6 to 12 years of age). o Drowsiness (only applicable to age stratum: 1 to 5 years of age). o Irritability/Fussiness (only applicable to age stratum: 1 to 5 years of age). o Loss of appetite (only applicable to age stratum: 1 to 5 years of age).

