### 15.3. SOLICITED AND UNSOLICITED ADVERSE EVENTS (AEs)

The following tables are planned for presentation for the Total Vaccinated Cohort:

- Overview of solicited and unsolicited AEs:
  - o These will be presented together with the overview of unsolicited AEs (refer to Section 15.1.2: All Unsolicited Adverse Events):
    - \*Any AE.
    - \*Any severe (grade 3) AE.
    - \*Any related AE.
    - \*Any severe (grade 3) related AE.
    - \*Any AE leading to premature study withdrawal.
    - \*Any Severe (grade 3) AE leading to premature study withdrawal.
    - \*Any Related AE leading to premature study withdrawal.
    - \*Any Severe (grade 3) AE related leading to premature study withdrawal.
- Solicited and unsolicited AEs experienced by at least 5% of subjects within the 30 day post-vaccination window, including the number of events:
  - o Multiple events are counted as multiple events for the calculation of the number of events (n\*).
  - o AEs will be presented by MedDRA System Organ Class and Preferred Term.
  - o SAEs will be excluded from this table.

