Reference: CS\_WI\_BS005

Effective Date: 01May2012

Copyright © 2012 Quintiles Transnational Corp. All rights reserved.

The contents of this document are confidential and proprietary to Quintiles Transnational Corp. Unauthorised use, disclosure or reproduction is strictly prohibited.

MedDRA 17.1 Preferred Term	Preferred Term Code	MedDRA 17.1 Preferred Term	Preferred Term Code
Increased tendency to bruise	10021688	Uterine haematoma	10063875
Increased tendency to bruise	10021688	Uterine haemorrhage	10046788
Induced abortion haemorrhage	10052844	Vaccination site bruising	10069484
Infusion site bruising	10059203	Vaccination site haematoma	10069472
Infusion site haematoma	10065463	Vaccination site haemorrhage	10069475
Infusion site haemorrhage	10065464	Vaginal haematoma	10046909
Injection site bruising	10022052	Vaginal haemorrhage	10046910
Injection site haematoma	10022066	Varicose vein ruptured	10046999
Injection site haemorrhage	10022067	Vascular pseudoaneurysm ruptured	10053949
Instillation site haematoma	10073609	Vascular purpura	10047097
Instillation site haemorrhage	10073610	Vascular rupture	10053649
Internal haemorrhage	10075192	Venous haemorrhage	10065441
Intestinal haematoma	10069829	Ventricle rupture	10047279
Intestinal haemorrhage	10059175	Vessel puncture site bruise	10063881
Intra-abdominal haematoma	10056457	Vessel puncture site haematoma	10065902
Intra-abdominal haemorrhage	10061249	Vessel puncture site haemorrhage	10054092
Intracerebral haematoma evacuation	10062025	Vitreous haematoma	10071936
Intracranial haematoma	10059491	Vitreous haemorrhage	10047655
Intracranial tumour haemorrhage	10022775	Vulval haematoma	10047756
Intraocular haematoma	10071934	Vulval haematoma evacuation	10047757
Intrapartum haemorrhage	10067703	Vulval haemorrhage	10063816
Intraventricular haemorrhage	10022840	Wound haematoma	10071504
Intraventricular haemorrhage neonatal	10022841	Wound haemorrhage	10051373

Document: CHAD3-004-EBO-Z\_Interim\_Final\_SAP\_v2\_0

Author: PPD Version Number: 2.0 Version Date: 14JUN2017

Template No: CS\_TP\_BS016 – Revision 3

Reference: CS\_WI\_BS005

Effective Date: 01May2012

Copyright © 2012 Quintiles Transnational Corp. All rights reserved.

The contents of this document are confidential and proprietary to Quintiles Transnational Corp. Unauthorised use, disclosure or reproduction is strictly prohibited.

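### In the combined table of common adverse events, SAP Table 6 drops the injection site from the solicited local reactions and files redness as a skin disorder

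*SAP*

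**What the plan says.** Protocol Table 16 defines three solicited local events, all tied to the place of injection: "Pain at injection site", and redness and swelling at the same place. SAP v2 Appendix 4 grades them on that basis.

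Under SAP v2 Section 15.2, data management does not code solicited events. Section 15.2.1 supplies the only coding step: "MedDRA System Organ Class as well as Preferred Term will be assigned based on Table 6: Solicited Adverse Events MedDRA Coding". The three local rows of Table 6, which are the same in SAP v1, read:

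| Solicited sign | System organ class | Preferred term |
|---|---|---|
| Redness | "Skin and subcutaneous tissue disorders" | Erythema |
| Swelling | "General disorders and administration site conditions" | Swelling |
| Pain | "General disorders and administration site conditions" | Pain |

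Two kinds of output then report solicited events. The incidence table in Section 15.2.2 gives the "Number and percentage (%) subjects with solicited AEs summarised by category and sign or symptom", and the order is fixed: "For all solicited AEs the categories and signs or symptoms will be sorted as listed below", with local signs first and general symptoms after. Section 15.3 adds a table that combines solicited and unsolicited events seen in at least 5% of subjects within 30 days of vaccination. For that table, "AEs will be presented by MedDRA System Organ Class and Preferred Term".

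**The concern.** The split between local and general events is basic to a reactogenicity report, and safety and reactogenicity are this trial's primary objective. Protocol Section 11.8 keeps the split even when solicited and unsolicited events are taken together, because it asks for the percentage of subjects with any local event and with any general event. A table of common events by class and term can be read on its own, so its terms should show which events are injection-site reactions.

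With Table 6 as written, they do not. A sore arm and an unsolicited report of generalised pain both become Pain. Redness at the injection site becomes Erythema under skin disorders, so a difference between vaccines in local redness would appear as a difference in skin disorders. A general term reported by very few children could also enter the table only because local reactions share its label.

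**Working it through.** The plan gives no figure to reproduce here. The check is to read Table 6 row by row and follow its codes into each planned output.

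**1. What Table 6 does to the local signs.**
- Preferred term without the site: redness, swelling and pain, 3 of 3.
- Class other than the one that covers administration-site conditions: redness, 1 of 3.
- Already in that class: swelling and pain, 2 of 3.

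**2. Whether site-specific terms exist.** They do. SAP Appendix 3, headed MedDRA 17.1, lists "Injection site bruising" separately from Contusion, and Injection site haematoma separately from Haematoma. Appendix 3 covers bleeding-related terms, so it shows the form of such terms. It does not list the ones needed for pain, erythema and swelling.

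**3. Which outputs use the codes.**

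| Output (SAP v2) | Organised by | Uses Table 6 codes for local signs? |
|---|---|---|
| Solicited overview, 15.2.2 | Separate local and general rows | No |
| Solicited incidence, severity and relationship, 15.2.2 | Category, then sign or symptom | No |
| Reactogenicity figures, 15.2.2 | Drawn separately for local and general | No |
| Unsolicited incidence tables, 15.1.2 | Class and term, unsolicited events only | No |
| Combined table of events in at least 5%, 15.3 | Class and term, with no local/general split stated | Yes |

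The description of one table relies on the codes.

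**4. How the 5% rule works in that table.** The SAP does not say whether the rule applies per group or overall, or at term or class level. Assume it applies to each preferred term within a planned group of about 300. The threshold is then 0.05 × 300 = 15 children. Suppose 1 child has unsolicited generalised erythema and 14 other children have injection-site redness. Then 1 + 14 = 15 and 15/300 = 5.0%, so Erythema is listed under skin disorders although only 1 child had the general event. The counts of 1 and 14 are assumed, to show the mechanism. The documents give no expected rates for either event.

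**5. What a correction would change.** It would change the labels of the three local signs in the Section 15.3 table, the class that holds redness, and which events share a row. No count or confidence interval in the solicited tables would move.

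**The case against.** The strongest reply is that this is a label in one descriptive table. The primary endpoint is each solicited local and general event, and the outputs that report it never use Table 6 codes. A reader can find the local reactions in the Section 15.2.2 tables and any unsolicited Pain, Swelling or Erythema in the Section 15.1.2 tables. All analyses are descriptive (Section 7.4), so no test rests on the label. The table, listing and figure shells, which Section 8 says set the format and content of the outputs, are not among the documents; a flag or footnote there cannot be ruled out. All of this stands. It limits the reach of the point but does not make the coding right.

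Three stronger readings are tempting, and the documents do not support them:

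- **That local reactions are reported throughout as body-wide events.** Step 3 shows otherwise.
- **That all three signs are in the wrong class, or that a size can be put on the inflation of skin disorders.** Only redness changes class. No rate is given for injection-site redness or for unsolicited skin events, and the level of the 5% filter is unstated.
- **That unsolicited administration-site events need recoding too.** These are coded in MedDRA, with the coding variables supplied by data management, and the form records whether the event was at the administration site (Section 15.1). Nothing shows that they lack site-specific terms.

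**Conclusion.** The point holds for the Section 15.3 table only. Followed as written, Table 6 makes that table merge injection-site reactions with unsolicited general events of the same term, and it counts injection-site redness as a skin disorder. All three local signs lose their site and one of the three moves class. The primary reactogenicity tables and figures and the unsolicited tables are unaffected.

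This rests on two assumptions: that the shells add no local/general marker to the Section 15.3 table, and that unsolicited events with the same preferred terms occur, which the merging and threshold effects need. The misplacement of redness does not need the second. No numerical size can be given from the documents. The severity is minor.

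**What to change.** Either of two changes is enough.

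1. In Table 6, replace the three local preferred terms with the site-specific terms for injection-site pain, erythema and swelling, and move redness to "General disorders and administration site conditions". That is three term cells plus one class cell, four in all. The exact term names and their class should be checked in the MedDRA version used. The documents do not reproduce them, and Appendix 3 shows several families (administration site, injection site, vaccination site) from which one must be chosen.
2. Leave Table 6 alone and split the Section 15.3 table into local and general rows.

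Neither needs new data. The cost is a small programming change and a final display that differs from the interim one, since Table 6 has stood unchanged since SAP v1. A footnote to the final table can state the difference.

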#### 15.2.2. ALL SOLICITED ADVERSE EVENTS

The following listing is planned for presentation for the Total Vaccinated Cohort:

- Solicited AEs.

The following tables are planned for presentation for the Total Vaccinated Cohort:

- Overview of Solicited AEs:
  - Number and percentage (%) of subjects in each of the following categories:
    - Solicited AE.
    - Solicited severe (grade 3) AE.
    - Solicited related AE.
    - Solicited severe (grade 3) related AE.
    - Solicited local AE.

Document: CHAD3-004-EBO-Z\_Interim\_Final\_SAP\_v2\_0  
 Author: PPD Version Number: 2.0 Version Date: 14JUN2017

Template No: CS\_TP\_BS016 – Revision 3  
 Effective Date: 01May2012

Reference: CS\_WI\_BS005

- Severe (grade 3) solicited local AE.
- Solicited general AE.
- Severe (grade 3) solicited general AE.
- Related solicited general AE.
- Severe (grade 3) related solicited general AE.
- Solicited AE leading to premature study withdrawal.
- Severe (grade 3) solicited AE leading to premature study withdrawal.
- Related solicited AE leading to premature study withdrawal.
- Severe (grade 3) related solicited AE leading to premature study withdrawal.
- o Percentage (%) of subjects will be calculated relative to the total number of subjects in the relevant analysis cohort, per treatment group with returned diary cards.
- o A 95% confidence interval (CI) for the proportion of subjects with AEs in each category will be obtained by using the exact binomial option.
- o Subjects with multiple events in each category are counted only once in each category.
- Incidence of solicited AEs:
  - o Number and percentage (%) subjects with solicited AEs summarised by category and sign or symptom.
- Incidence of solicited AEs by severity:
  - o Number and percentage (%) subjects with solicited AEs summarised by category, sign or symptom and severity.
  - o This table will be repeated for related solicited AEs (including general solicited AEs only).
- Incidence of solicited AEs by relationship:
  - o Number and percentage (%) subjects with solicited AEs summarised by category, sign or symptom and relationship.
- Duration of fever (days):
  - o Descriptive statistics for the duration of fever will be provided, based on all subjects with at least one fever event reported.
- Onset Day of Fever during 7-day Follow-up Period After Vaccination on Day 0
  - o Number and percentage (%) subjects with solicited fever summarised by earliest onset day (Day 0 to Day 6) following Day 0 study vaccination.
  - o Subjects with multiple events are considered only once at the earliest onset day. o % is based on the number of subject who reported fever in each category.

The following figures are planned for presentation for the Total Vaccinated Cohort:

- Reactogenicity events:
  - o Percentage of subjects presenting solicited AEs along with the 95% CI will be presented for all solicited events as well as Grade 3 or 4 events on the same figure (nested bar chart). o The bars will be presented separately for each treatment group. o This figure will be presented separately for

Document: CHAD3-004-EBO-Z\_Interim\_Final\_SAP\_v2\_0

Author: PPD Version Number: 2.0 Version Date: 14JUN2017

Template No: CS\_TP\_BS016 – Revision 3

Reference: CS\_WI\_BS005

Effective Date: 01May2012

- the local and general solicited AEs. o This figure will be repeated for the pooled data following the EBO-Z vaccination.
- Fever incidences per study day following Day 0 vaccination:
  - o Percentage of subjects presenting solicited fever along with the 95% CI will be presented for all solicited fever events as well as Grade 3 or 4 fever on the same figure (nested bar chart).
  - o The figure will be presenting the earliest study of fever onset. o The bars will be presented separately for each treatment group. o These figures will only include solicited fever within the reporting period following Day 0 vaccination.

For all solicited AEs the categories and signs or symptoms will be sorted as listed below:

Local:

- o Pain. o Redness.
- o Swelling.
- General:
  - o Fever. o Fatigue (only applicable to age strata: 13 to 17 years of age and 6 to 12 years of age).
  - o Gastrointestinal symptoms (only applicable to age strata: 13 to 17 years of age and 6 to 12 years of age).
  - o Headache (only applicable to age strata: 13 to 17 years of age and 6 to 12 years of age). o Drowsiness (only applicable to age stratum: 1 to 5 years of age). o Irritability/Fussiness (only applicable to age stratum: 1 to 5 years of age). o Loss of appetite (only applicable to age stratum: 1 to 5 years of age).

All solicited AE incidence tables will include AEs reported during the collection period following the vaccination at Day 0. Therefore, solicited AEs reported during the collection period following the Month 6 vaccination will be excluded from the solicited AE incidence tables, unless otherwise specified.

All solicited AE incidence tables will be repeated for the following pooling of AEs:

- AEs following the active ChAd3-EBO-Z vaccination; hence:
  - o EBO-Z/MENACWY-TT subjects: Solicited AEs within the reporting window following Day 0 vaccination.
  - o MENACWY-TT/EBO-Z subjects: Solicited AEs within the reporting window following Month 6 vaccination.

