## **11. STATISTICAL METHODS**

### **11.1. Primary endpoints**

- Occurrence of each solicited local and general AE, during a 7-day follow-up period after each vaccination in all subjects, in both groups.
- Occurrence of any unsolicited AE, during a 30-day follow-up period after each vaccination (*i.e.*, the day of vaccination and 29 subsequent days), in all subjects, in both groups.

- Occurrence of haematological (CBC, including differential count and platelet count) and biochemical (ALT, creatinine) laboratory abnormalities at Screening, Day 3, Day 6, Day 30, Month 6, Month 6 + 6 days, Month 6 + 30 days and Month 12 in all subjects in both groups.
- ***Occurrence of clinical symptoms of thrombocytopenia (AE of specific interest), during a 7-day follow-up period after vaccination at Day 0 (i.e., Day 0 up to Day 6), in all subjects, in both groups.***  

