### **11.8. Analysis of safety**

The analysis will be performed on the TVC.

All analyses will be descriptive. Analyses will be performed by age stratum (1 to 5 years, 6 to 12 years, 13 to 17 years) and overall.

In a first step, the safety results will be presented by treatment administered at Day 0 (ChAd3-EBO-Z vaccine [300 subjects] versus *Nimenrix* [300 subjects]). In a second step, all **available** data post-vaccination with the investigational ChAd3-EBO-Z vaccine (ChAd3-EBO-Z vaccine at Day 0 [300 subjects] and ChAd3-EBO-Z vaccine at Month 6 [300 subjects]) will be pooled (600 subjects). The latter aggregated data cannot be presented versus control because of the administration of the investigational ChAd3-EBO-Z vaccine to the children in the Group MENACWY-TT/ EBO-Z, who initially received *Nimenrix* (population overlap).

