### **11.10. Interpretation of analyses**

Comparative analyses will be descriptive with the aim to characterise the difference in reactogenicity/ safety/ immunogenicity between groups.

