#### 2.1.2. PRIMARY ENDPOINTS

- Occurrence of each solicited local and general adverse event (AE), during a 7-day follow-up period after each vaccination (that is, the day of vaccination and 6 subsequent days), in all subjects, in both groups.
- Occurrence of any unsolicited AE, during a 30-day follow-up period after each vaccination (that is, the day of vaccination and 29 subsequent days), in all subjects, in both groups.
- Occurrence of haematological (complete blood count [CBC], including differential count and platelet count) and biochemical (alanine aminotransferase [ALT], creatinine) laboratory abnormalities at Screening, Day 3, Day 6, Day 30, Month 6, Month 6 + 6 days, Month 6 + 30 days and Month 12 in all subjects, in both groups.
- Occurrence of clinical symptoms of thrombocytopenia (AE of specific interest), during a 7-day follow-up period after vaccination at Day 0 (that is, Day 0 up to Day 6), in all subjects, in both groups.
- Occurrence of any serious adverse event (SAE), in all subjects, in both groups.

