## 3.3. CHANGES TO ANALYSIS FROM PROTOCOL

None.

Document: CHAD3-004-EBO-Z\_Interim\_Final\_SAP\_v2\_0

Author: PPD Version Number: 2.0 Version Date: 14JUN2017

Template No: CS\_TP\_BS016 – Revision 3

Reference: CS\_WI\_BS005

Effective Date: 01May2012

Copyright © 2012 Quintiles Transnational Corp. All rights reserved.

The contents of this document are confidential and proprietary to Quintiles Transnational Corp. Unauthorised use, disclosure or reproduction is strictly prohibited.

---

Document: CHAD3-004-EBO-Z\_Interim\_Final\_SAP\_v2\_0  
Author: PPD Version Number: 2.0 Version Date: 14JUN2017

Template No: CS\_TP\_BS016 – Revision 3  
Effective Date: 01May2012

Reference: CS\_WI\_BS005

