All unsolicited AE incidence tables will include AEs reported during the collection period following the vaccination at Day 0. Therefore AEs reported during the collection period following the Month 6 vaccination will be excluded from the unsolicited AE incidence tables, unless otherwise specified.

All unsolicited AE incidence tables will be repeated for the following pooling of AEs, presented per age stratum:

- AEs following the active ChAd3-EBO-Z vaccination; hence:

- o EBO-Z/MENACWY-TT subjects: Unsolicited AEs within the reporting window following Day 0 vaccination.
- o MENACWY-TT/EBO-Z subjects: Unsolicited AEs within the reporting window following Month 6 vaccination.

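### Solicited and non-serious unsolicited AEs after the Month 6 Nimenrix dose have no incidence table in the SAP text, and no ChAd3-EBO-Z minus Nimenrix difference is estimated at Day 0

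*SAP*

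**What the plan says.** **Endpoints.** Protocol 11.1 lists "Occurrence of each solicited local and general AE, during a 7-day follow-up period after each vaccination in all subjects, in both groups" and "Occurrence of any unsolicited AE, during a 30-day follow-up period after each vaccination". SAP version 2.0, section 2.1.2, keeps this scope: "during a 7-day follow-up period after each vaccination (that is, the day of vaccination and 6 subsequent days), in all subjects, in both groups".

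**Tables.** SAP 15.2.2 says that "solicited AEs reported during the collection period following the Month 6 vaccination will be excluded from the solicited AE incidence tables, unless otherwise specified". SAP 15.1.2 says that "AEs reported during the collection period following the Month 6 vaccination will be excluded from the unsolicited AE incidence tables, unless otherwise specified". In both sections the incidence tables are then repeated for AEs after ChAd3-EBO-Z, pooling Day 0 in Group EBO-Z/MENACWY-TT with Month 6 in Group MENACWY-TT/EBO-Z.

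**Source of the two steps.** Protocol 11.8 presents safety by Day 0 treatment first, then pools all data after ChAd3-EBO-Z. On the pooled data it says: "The latter aggregated data cannot be presented versus control because of the administration of the investigational ChAd3-EBO-Z vaccine". It gives population overlap as the reason.

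**Comparison.** Protocol 11.10 states: "Comparative analyses will be descriptive with the aim to characterise the difference in reactogenicity/ safety/ immunogenicity between groups". The overview tables in SAP 15.1.2 and 15.2.2 specify an exact binomial 95% CI for each group's proportion. No difference, and no interval for one, is specified.

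**Record of changes.** SAP version 2.0, section 3.3 ("CHANGES TO ANALYSIS FROM PROTOCOL"), reports none. The Day 0 restriction is absent from version 1.0 and is not mentioned in the version 2.0 modification history.

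**The concern.** Two of the five primary endpoints are defined over both vaccinations in both groups, but one of the four group-by-period cells, Nimenrix at Month 6, has no incidence table assigned to it. The SAP also disagrees with itself. Section 15.1.6 says that AE incidence tables follow its Table 5, where the unsolicited window applies to each vaccination, while 15.1.2 stops at Day 0. Section 15.2.1 derives a dose at onset of Nimenrix at Month 6 for solicited AEs, and no table is named that uses it. Two programmers could reasonably produce different outputs.

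The second matter is what the control is for. Protocol 1.2.2.3 says Nimenrix will support the safety comparison, and 11.10 sets out to describe a difference. Two separate one-sample intervals do not give an interval for that difference, so the reader must judge it by eye.

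**Working it through.** **1. The plan's own figure.** Protocol Table 22 gives exact (Clopper-Pearson) 95% CIs at n = 300. With 0 events the upper limit is 1 − 0.025^(1/300) = 0.0122, as printed; 15/300 gives 0.0283 to 0.0811, as printed. All seven rows reproduce. The table describes the precision of one group's rate. The documents give no precision for a difference.

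**2. Dose windows with a planned incidence table** (target enrolment, no dropout):

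| Period | Vaccine | Windows | Incidence table in SAP text |
|---|---|---|---|
| Day 0 | ChAd3-EBO-Z | 300 | main and pooled |
| Day 0 | Nimenrix | 300 | main |
| Month 6 | ChAd3-EBO-Z | 300 | pooled only |
| Month 6 | Nimenrix | 300 | none named |

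Covered: 900/1,200 = 75%. Not covered: 300/1,200 = 25%. Including the missing cell would give 600 Nimenrix windows, and the upper limit at 0 events would fall from 0.0122 to 1 − 0.025^(1/600) = 0.0061.

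**3. Precision of a Day 0 difference.** The documents give no expected AE rates, so I assume equal rates p in both groups, at 5% and 50% (both appear in Table 22). Half-width = 1.96 × √[2p(1 − p)/n], n per group.

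- 300 v 300 (pain, redness, swelling, fever, any unsolicited AE): p = 5%, 1.96 × √(0.095/300) = 3.5 points; p = 50%, 1.96 × √(0.5/300) = 8.0 points.
- 200 v 200 (fatigue, headache, gastrointestinal symptoms, solicited only from 6 years): 4.3 to 9.8 points.
- 100 v 100 (drowsiness, irritability/fussiness, loss of appetite, solicited only at 1 to 5 years; also any single age stratum): 6.0 to 13.9 points.

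Six of the ten solicited AEs are age-specific, so the 300 v 300 figure does not apply to them.

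**4. Why separate intervals are a poor substitute.** For 150/300, Table 22 gives 0.4420 to 0.5580, a half-width of 5.8 points. Two such intervals near 50% stop overlapping only when the rates are about 2 × 5.8 = 11.6 points apart. An interval for the difference has a half-width of 8.0 points.

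**5. Using both periods.** Every child is due both vaccines. With assumed within-child correlation ρ, half-width = 1.96 × √[2p(1 − p)(1 − ρ)/600]. At p = 5% this is 2.5 points for ρ = 0 and 1.9 for ρ = 0.4; at p = 50%, 5.7 and 4.4. The gain requires ρ of 0 or more and no dropout. Neither is given in the documents.

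**The case against.** The other side has a strong case, and much of it stands.

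- **Month 6 data are not discarded.** Every ChAd3-EBO-Z dose is tabulated, which is what the primary objective is about. SAEs are tabulated by dose, including Nimenrix (SAP 15.1.5), and listings keep all events. Laboratory tables are not limited to Day 0, and the AESI endpoint is Day 0 only by protocol. The gap concerns the licensed control in one period.
- **The SAP did not invent the two steps.** They come from Protocol 11.8. The tension is between Protocol 11.1 and 11.8, and the SAP carries it forward.
- **The exclusion has an escape clause.** It applies unless otherwise specified. The overview tables and the table of AEs in at least 5% of subjects carry no explicit Day 0 limit, and the TLF shells, not available here, may add outputs. The claim therefore has to be confined to the SAP text. Those tables do not fill the gap as written, because none is specified to show Month 6 Nimenrix separately.
- **The study is descriptive.** SAP 7.4 disclaims confirmatory objectives, and side-by-side rates do describe the groups. But a risk difference with a CI is itself descriptive and needs no hypothesis test, so this does not answer Protocol 11.10.

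A reader might infer that a ready controlled comparison is lost. The documents do not support that. The randomised, observer-blind Day 0 groups, 300 v 300, are presented by group. Month 6 would be weaker evidence: under Protocol 5.3 the study becomes single-blind at the interim analysis and separate vaccine-administration staff are described only for Day 0; each child has already had the other vaccine; and withdrawals and Month 6 contraindications reduce the numbers. Population overlap rules out treating the pooled data as two independent samples. It does not rule out a Month 6 between-group table or a clustered analysis.

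**Conclusion.** The point holds in this form: for two of the five primary endpoints, one of the four group-by-period cells has no incidence table in the SAP text. That is about 300 of 1,200 dose windows, at target enrolment and without dropout. Sections 15.1.2 and 15.2.2 conflict with Table 5 in 15.1.6 and with the dose-at-onset derivation in 15.2.1. In addition, no between-vaccine difference is estimated, although Protocol 11.10 aims to characterise one.

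The half-widths in the working are conditional on assumed rates and full enrolment. They show what the existing sample can deliver and imply no change in sample size.

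Two stronger readings should be resisted. It would be wrong to say that all Month 6 events are removed, because ChAd3-EBO-Z events return in the pooled tables. It would also be wrong to call the restriction purely a SAP departure, because Protocol 11.8 sets the two-step presentation. What can be said is that the restriction narrows the 11.1 endpoint as tabulated and is recorded nowhere. This should be corrected; it does not threaten the main Day 0 safety presentation.

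**What to change.** 1. Add solicited and unsolicited AE incidence tables for the Month 6 period by vaccine received, with Nimenrix shown separately.
2. Add descriptive Day 0 risk differences, ChAd3-EBO-Z minus Nimenrix, with 95% CIs for each solicited AE, Grade 3 AEs and any unsolicited AE. Stratify by age stratum (for example Mantel-Haenszel) where the AE is collected in more than one stratum. For the three AEs collected only at 1 to 5 years, use an unstratified interval within that stratum (for example Miettinen-Nurminen).
3. If a Month 6 between-group estimate or a two-period estimate is given, label it supportive. For two periods, use a model with period and age stratum and with the child as cluster (for example GEE). State the blinding and prior-exposure limits beside it.
4. Reconcile Protocol 11.1 with 11.8, and SAP 15.1.2 and 15.2.2 with 15.1.6. Record the Day 0 restriction in SAP 3.3 and in the modification history.

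The cost is SAP wording, table shells and programming, with no new data. Version 2.0 already contains analyses first run ad hoc for the interim, so these additions should be dated and labelled descriptive, with no adjustment for the number of AEs compared.
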